
The Teva DHP is a system that stores and transfers health data collected from the App and the inhaler. The cloud solution automatically synchronizes with the App after every events captured and/or at predetermined time periods/intervals. An internet connection to the smart device (eg, via wireless or cellular phone network) is required in order for communication to be established between the App and the cloud solution.
 
The phone camera will be used for scanning and pairing. The cloud solution will not send any notifications to the App. The cloud solution does not create, modify, or delete patient information.
 
By consenting to enrollment in the study and approving the privacy policy and terms of use, the patient accepts data synchronization with the cloud solution. If a patient does not provide consent to synchronize his/her App, no data will be transmitted to the cloud solution. Patient privacy will be maintained according to the laws and regulations, and patient identifiers will be substituted to maintain a patient's privacy to reviewers of the data.
	
The Teva DHP is a system that stores and transfers health data collected from the App. The cloud solution automatically synchronizes with the App after events and/or at predetermined time periods/intervals. An internet connection to the smart device (eg, wireless or cellular phone network) is required in order for communication to be established between the App and the cloud solution. The cloud solution will not send any notifications to the App. The cloud solution does not create, modify, or delete patient information
 
Patient privacy will be maintained according to the laws and regulations, and patient identifiers will be substituted to maintain a patient's privacy to reviewers of the data.
	
Paragraphs reordered and language revised for clarity. Deleted language in this section and new language added to Section 5.1.1 for better placement within the document.

Original text with changes shown	New wording	Reason/Justification for change
Section 5.1.2.3 Dashboard		

The data available on the dashboard are the inhaler data from the App and patient self-assessments, and environmental information received by the App. By default, data are not available on the dashboard (although stored on the cloud), unless the patient is required per the treatment group and gives consent to sharing of the data with the HCP in the informed consent.
	
The data available on the dashboard are the inhaler data from the App and patient self-assessments. The patient has no interaction with the dashboard. Teva personnel will have no access to the dashboard.
	
Environmental information included in error and now deleted. Deleted consent language and new language added to Section 5.1.1.

Section 5.2.1 Storage and Security (Other section affected by this change: Section 5.8)		

The investigational center personnel are responsible for acknowledging receipt of the IMP using the interactive response technology a Randomization and Trial Supply Management (RTSM) system.
	
The investigational center personnel are responsible for acknowledging receipt of the IMP using a Randomization and Trial Supply Management (RTSM) system.
	
Revised to make consistent with text used in the protocol.

Section 6.1.1 Asthma Control Test (Other sections affected by this change: Sections 6.1.2 and 6.1.3)		

The self-administered version of the ACT will be answered by the patients at the investigational center at Visit 1, and Visit 2, and at any unscheduled visit or at the Early Termination visit.
	
The self-administered version of the ACT will be answered by the patients at the investigational center at Visit 1, Visit 2, or at the Early Termination visit.
	
Corrected the visits when the questionnaires should be given to patients.

Section 6.1.4 System Usability Questionnaire		

The SUS will be answered by patients in the DS group, 18 years of age or older, at Visit 2, or at the ET visit. The SUS will be completed after all other questionnaires.
 
A SUS will be completed by investigational center personnel, regarding the use of the dashboard, at the end of the study.
	
The SUS will be answered by patients in the DS group, 18 years of age or older, at Visit 2, or at the ET visit. The SUS will be completed after all other questionnaires.
 
A SUS will be completed by investigational center personnel, regarding the use of the dashboard, at the end of the study.
	
Clarified when the SUS will be completed by patients and investigational center personnel.

Section 7.1.1 Definition of an Adverse Event		

An asthma exacerbation CAE will be defined by 1 of the following: 1) a reduction in FEV₁ of 20% or greater, 2) 1) in-patient hospitalization because of asthma, 3) emergency treatment because of asthma, or 4) use of prednisone or systemic
	
A CAE will be defined by 1 of the following: 1) in-patient hospitalization because of asthma, 2) emergency treatment because of asthma, 3) use of prednisone or systemic corticosteroids for 3
	
Moved contents of Section 7.1.7 to this section, deleted first paragraph, and reordered and corrected errors.

Original text with changes shown	New wording	Reason/Justification for change

corticosteroids for 3 days or more, or 4) a reduction in FEV₁ of 20% or greater. Patients will be instructed to contact the study investigational center in the event of an asthma exacerbation CAE.
 
All CAE events require documentation by the investigator in the CAE Exacerbation Page in the CRF, as well as in the adverse event CRF. All evaluations entered into the CAE Exacerbation Page require the investigational center to obtain source documentation of all asthma exacerbations CAEs that occur during the treatment period to confirm the accuracy of the information obtained from the patient.-Any CAE that meets serious adverse event criteria will be reported as a serious adverse event (Section 7.1.5.1).
 
The process for reporting a protocol defined adverse event of special interest is the same as that for reporting a serious adverse event (Section 7.1.5.3). Protocol defined adverse events of special interest are to be reported to GPSP and can be either serious or nonserious, according to the criteria outlined in Section 7.1.5.1.
	
days or more, or 4) a reduction in FEV₁ of 20% or greater. Patients will be instructed to contact the study investigational center in the event of a CAE.
 
All CAE events require documentation by the investigator in the CAE Page in the CRF, as well as in the adverse event CRF. All evaluations entered into the CAE Page require the investigational center to obtain source documentation of all CAEs that occur during the treatment period to confirm the accuracy of the information obtained from the patient.-Any CAE that meets serious adverse event criteria will be reported as a serious adverse event (Section 7.1.5.1).
	
Section 10.1 Sample Size and Power Considerations		

The recommended sample size for the study is 150 evaluable patients per group (4030 investigational centers, with each investigational center enrolling at least 10 patients), 300 patients in total.
	
The recommended sample size for the study is 150 evaluable patients per group (30 investigational centers, with each investigational center enrolling at least 10 patients), 300 patients in total.
	
This change was made to correct the number of investigational centers and the number of patients to be enrolled at each investigational center.

Section 10.5.4.1 Primary Efficacy Analysis		

2. A binary distribution is assumed for the primary endpoint. Patients who discontinue early due to technology failure, disliking the digital platform, disease worsening, adverse experience or disliking the IMP will be counted as treatment failures. Patients who discontinue early due to reasons not
	
2. A binary distribution is assumed for the primary endpoint. Patients who discontinue early due to technology failure, disliking the digital platform, disease worsening, adverse experience or disliking the IMP
	
The equation was changed because baseline ACT value is another factor we need to adjust assuming a correlation between change from baseline and baseline ACT scores.

[figure not shown]
[figure not shown]
[figure not shown]
[figure not shown]
[figure not shown]
[figure not shown]
Original text with changes shown	New wording	Reason/Justification for change

associated with these reasons will be assumed to have outcomes similar to others in their treatment group. For those who discontinue early not due to these reasons, the ACT value assessed at the ET visit will be used.
 
3. Intercurrent events of withdrawal due to disliking technology, technology failure, disease worsening, adverse experiences, or disliking the IMP will be captured through definition of analysis set.
 
4.3. Summary measure: A successful differentiation between the 2 groups will be determined by a Bayesian posterior probability for β_1 greater than 0.95 (1-sided). The following statistical methods will be utilized:
 
Logistic regression model allowing for different response rates at enrolling investigational centers will be used for testing the hypothesis $H_0: \beta_1 = 0, H_1: \beta_1 > 0$ in the following model:
 $\ln \frac{p_{ij}}{1 - p_{ij}} = \delta_j + \beta_0 \text{baseline ACT value} + \beta_1 x_{ij}$ 
Where p_{ij} denotes response proportion in each group for each investigational center.
 
Where $i = \text{treatment group}, j = \text{investigational center}, x_{ij} = \text{treatment group } i \text{ for investigational center } j, p_{ij} = \text{response proportion of treatment group } i \text{ in investigational center } j.$
	
will be counted as treatment failures. For those who discontinue early not due to these reasons, the ACT value assessed at the ET visit will be used.
 
3. Summary measure: A successful differentiation between the 2 groups will be determined by a Bayesian posterior probability for β_1 greater than 0.95 (1-sided). The following statistical methods will be utilized:
 
Logistic regression model allowing for different response rates at enrolling investigational centers will be used for testing the hypothesis $H_0: \beta_1 = 0, H_1: \beta_1 > 0$ in the following model:
 $\ln \frac{p_{ij}}{1 - p_{ij}} = \delta_j + \beta_0 \text{baseline ACT value} + \beta_1 x_{ij}$ 
Where $i = \text{treatment group}, j = \text{investigational center}, x_{ij} = \text{treatment group } i \text{ for investigational center } j, p_{ij} = \text{response proportion of treatment group } i \text{ in investigational center } j.$
	
Number 3 was deleted because it is no longer relevant since number 2 already covers all the reasons for early termination.

Section 10.5.4.3 Secondary Efficacy Analysis (Other section affected by this change: Section 10.7)		

For continuous variables, descriptive statistics (number [n], mean, standard deviation, median, minimum, and maximum) will be provided for actual observed values and changes from baseline to each time point.
	
For continuous variables, descriptive statistics (number [n], mean, standard deviation, median, minimum, and maximum) will be provided for observed values and changes from baseline to each time point.
	
Word changed for accuracy.

Original text with changes shown	New wording	Reason/Justification for change
Appendix A. Clinical Laboratories and Other Departments and Institutions		
Teva Pharmaceuticals [REDACTED] Teva Pharmaceuticals [REDACTED]	Teva Pharmaceuticals [REDACTED] [REDACTED]	Change of Safety Physician.
Appendix B. Study Procedures and Assessments by Visit. 1. Procedures for Screening/Baseline Visit (Visit 1, Day 1)		

 administer pre-intervention Asthma Control Test (ACT) to all patients administer Brief Medication Questionnaire (BMQ) and Brief Illness Perception Questionnaire (BIPQ) to patients 18 years of age or older create and provide patient-specific unique email account to patients in the Digital System (DS) group for registration and onboarding in the application (App) reimburse or dispense voucher to patients in the concurrent control (CC) group 	
 administer pre-intervention Asthma Control Test (ACT) to all patients administer Brief Medication Questionnaire (BMQ) and Brief Illness Perception Questionnaire (BIPQ) to patients 18 years of age or older create and provide patient-specific unique email account to patients in the Digital System (DS) group for registration and onboarding in the application (App) reimburse or dispense voucher to patients in the concurrent control (CC) group 	Text revised to match Table 3.

Original text with changes shown	New wording	Reason/Justification for change
Appendix B, Study Procedures and Assessments by Visit, 3. Procedures for End of Study/Early Termination Visit (Visit 2, Day 84 + up to 7 days)		

 • iHCP asks Asthma Management questions • administer ACT to all patients and BMQ and BIPQ, to all patients, 18 years of age or older • administer System Usability Scale (SUS) to patients in the DS group, 18 years of age or older and investigational center personnel 	
 • iHCP asks Asthma Management questions • administer ACT to all patients and BMQ and BIPQ, to patients, 18 years of age or older • administer System Usability Scales (SUS) to patients in the DS group, 18 years of age or older, and investigational center personnel 	Text added to match text in Table 3.
Appendix B. Study Procedures and Assessments by Visit, 4. Unscheduled Visits or Phone Calls		

The following procedures and assessments will be performed at Procedures performed during unscheduled visits and unscheduled phone calls include:
 
 • conducting adverse events and adverse device effects inquiry • conducting concomitant medication inquiry • recording reason for unscheduled visit or call • measuring vital signs (unscheduled visit only) • ACT, BMQ, and BIPQ (unscheduled visit only) • dispensing Albuterol eMDPI as needed (unscheduled visit only) 	
The following procedures and assessments will be performed at unscheduled visits and unscheduled phone calls:
 
 • conduct adverse events and adverse device effects inquiry • conduct concomitant medication inquiry • record reason for unscheduled visit or call • measure vital signs (unscheduled visit only) • dispense Albuterol eMDPI as needed 	Text revised to match previous sections and to match Table 3

Original text with changes shown	New wording	Reason/Justification for change

 • performing Albuterol eMDPI collection and accountability (unscheduled visit only) • reviewing patient compliance • iHCP asks Asthma management questions 	
 • (unscheduled visit only) • perform Albuterol eMDPI collection and accountability (unscheduled visit only) • review patient compliance • iHCP asks Asthma management questions 	
Appendix B, Study Procedures and Assessments by Visit, 5. Procedures for Follow-up Telephone Call (Day 98 + 7 days)		
	
The following procedures and assessments will be performed at the follow-up telephone call:
 
 • conduct adverse events and adverse device effects inquiry • conduct concomitant medication inquiry • confirm that the patient has returned to previous asthma treatment 	Text added to match text in Table 3.

APPENDIX B. STUDY PROCEDURES AND ASSESSMENTS BY VISIT

1. Procedures for Screening/Baseline Visit (Visit 1, Day 1)²

The following procedures and assessments will be performed at Visit 1:

- obtain written informed consent/assent
- review inclusion and exclusion criteria
- obtain medical history
- obtain current medication and treatment history related to asthma
- measure vital signs
- conduct adverse events and adverse device effects inquiry
- inform patients of study restrictions and compliance requirements
- administer pre-intervention Asthma Control Test (ACT) to all patients
- administer Beliefs about Medicines Questionnaire (BMQ) and Brief Illness Perception Questionnaire (BIPQ) to patients 18 years of age or older
- randomize and assign patient number
- create and provide patient-specific unique email account to patients in the Digital System (DS) group for registration and onboarding in the application (App)
- train patients in the DS group on use and proper technique of the albuterol multidose dry powder inhaler with integrated electronic module (Albuterol eMDPI)
- dispense Albuterol eMDPI to patients in the DS group
- reimburse or dispense voucher to patients in the concurrent control (CC) group

2. Procedures for Treatment Period (Day 1 through Day 84)

The following procedures and assessments will be performed during the Treatment Period:

- resupply Albuterol eMDPI, if necessary

3. Procedures for End of Treatment/Early Termination Visit (Visit 2, Day 84 + up to 7 days)

The following procedures and assessments will be performed at Visit 2:

- conduct adverse events and adverse device effects inquiry
- conduct concomitant medication inquiry
- measure vital signs
- iHCP asks Asthma Management questions

² Patients may be enrolled up to 7 days after screening.

- administer ACT to all patients and BMQ and BIPQ, to patients, 18 years of age or older
- administer System Usability Scale (SUS) to patients in the DS group, 18 years of age or older, and investigational center personnel
- perform Albuterol eMDPI collection and accountability
- remove the App from the patient's smart device

4. Procedures for Clinically Driven Assessment(s) (If Necessary)

A Clinically Driven Assessment, which can either be via telephone or an on-site visit, may be performed at any time during the study at the patient's request and as deemed necessary by the investigator. For DS patients, the investigator will have access to information from the Albuterol eMDPI on the patient's SABA use and inhalation technique through the dashboard. If the investigator meets with or calls the patient as a result of an interaction with the dashboard, this will be captured as a Clinically Driven Assessment.

The date and reason for the Clinically Driven Assessment (eg, treatment step up, treatment step down, adherence discussion, treatment for an asthma exacerbation, or other clinical encounters generated by the data from the Albuterol eMDPI), as well as any other data obtained from procedures and assessments, will be recorded in the patient's source documents and the case report form (CRF) for patients in both groups, during the 12-week treatment period.

The following procedures and assessments will be performed at a Clinically Driven Assessment:

- conduct adverse events and adverse device effects inquiry
- conduct concomitant medication inquiry
- iHCP asks Asthma Management questions
- dispense Albuterol eMDPI, as needed (if on-site and necessary)

Other procedures and assessments may be performed at the discretion of the investigator.

5. Procedures for an Unscheduled Investigational Medicinal Product Dispensing Visit

The following procedures and assessments will be performed at an unscheduled IMP dispensing visit:

- conduct adverse events and adverse device effects inquiry
- conduct concomitant medication inquiry
- perform Albuterol eMDPI collection and accountability
- dispense test investigational medicinal product (IMP) to DS group patients

6. Procedures for Follow-up Telephone Call (Day 98 + 7 days)

The following procedures and assessments will be performed at the follow-up telephone call:

- conduct adverse events and adverse device effects inquiry

- conduct concomitant medication inquiry
- for DS group patients, confirm that the patient has returned to previous asthma treatment

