5.1.1. Test Investigational Medicinal Product

[figure not shown]
Albuterol eMDPI (marketed in the US as PROAIR DIGIHALER) is an inhalation-driven eMDPI containing a blend of albuterol sulfate and alpha-lactose monohydrate. The inhaler contains 200 actuations, each delivering 90 mcg of albuterol base ex-mouthpiece; the inhaler is equipped with a dose counter that shows only even numbers and counts down to “0.”

The plastic inhaler comprises a reservoir containing inhalation powder, a metering system, a mouthpiece with dust cover, and an eModule sitting on top of the drug-delivery compartment. Teva has developed the eModule as part of a system to assist a patient with asthma to appropriately use the eMDPI inhaler. The system is described in more practical terms as an inhaler with an integrated data logger capable of storing and transmitting timestamped data to support the data logging functionality.

The on-board electronics and power source are fully integrated into the eMDPI and are designed to operate for the life of the inhaler without intervention, ie, the battery does not require replacement or recharging.

The addition of the required electronics has no impact on the pharmaceutical performance of the inhaler or on the required user steps to take a dose. A schematic of the inhaler with the additional eModule is shown in [Figure 3](#).

Figure 3: Current Inhaler (Left) Versus Inhaler with Additional Electronics Module (Right)

Additional details may be found in [Table 4](#) and in the IB.

The information from the eModule may be transmitted wirelessly (Bluetooth Low Energy) to an App. From the App, data may be transmitted to the DHP, which consists of a Cloud solution, and then to a dashboard. This allows the patient and/or the caregiver to track when and how well the inhaler was used.

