By consenting to enroll in the study, the patient must also download the smart device App (with the assistance of investigational center personnel), accept the smart device App's Privacy Notice and Terms of Use, and also agree to share his/her data to a provider-facing dashboard utilized by the iHCP and investigational center study team. An ICF will be provided to the patients which will elaborate, among other ways, Teva's ways of use and storing of patient data collected through the smart device App. The patient will be entering into a direct contractual relationship with Teva which will govern, among other things, Teva's rights to use and store patient data collected through the smart device App. If the patient does not accept the smart device App's Privacy Notice and Terms of Use and does not also agree to share their data to the provider-facing dashboard utilized by the iHCP and investigational center study team, then the patient cannot enroll in the study. At the end of treatment/ET visit (Visit 2), investigational center personnel will remove the App from the patient's smart device.

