5.2.3. Accountability

Each IMP shipment will include a packing slip listing the contents of the shipment and any applicable forms.

The investigator is responsible for ensuring that deliveries of IMP for initial distribution to patients and other study materials from the sponsor are correctly received, recorded, handled, and safely and properly stored in accordance with national and local regulations, and used in accordance with this protocol.

Only patients enrolled in the study may receive IMP, and only authorized personnel at the investigational center may supply or administer IMP. All IMP must be stored in a secure, environmentally controlled, and monitored (manual or automated) area in accordance with the labeled storage conditions or appropriate instructions with access limited to the investigator and authorized personnel at the investigational center. The investigator (or designee) will instruct the patient to store the IMP according to the instructions on the label, if applicable; or will give instructions in an appropriate form. Patients will be instructed to return all IMP (empty, partially used, and unused inhalers) to the investigational center at end of treatment (Visit 2) or at the ET visit.

The investigator, institution, or the head of the medical institution (where applicable) is responsible for IMP accountability, reconciliation, and record maintenance (ie, receipt, reconciliation, and final disposition records). Patients will return all inhalers at the end of the study to the investigational center for reconciliation.

A record of IMP accountability (ie, IMP and other study materials received, used, retained, and returned) must be prepared and signed by the principal investigator or designee, with an account given for any discrepancies. All empty, partially used, and unused inhalers will be collected at the end of the study and will be returned to the sponsor or designee per sponsor instructions.

Further guidance and information are provided in the Study Pharmacy Manual.

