5.2. Patient Disposition

Patients screened and screened but not randomized (with reason not randomized) will be summarized only for all patients using patient counts. Patients in the ITT analysis set, ITT analysis set who did not attempt to download the App, ITT analysis set who did not use the inhaler, safety analysis set, and mITT analysis set, patients who completed and withdrew from treatment (with reason for withdrawing), and patients who completed and withdrew from the study (with reason for withdrawal) will be summarized using descriptive statistics. The summary will be based on all patients. The denominator for calculating the percentages will be the number of patients in the ITT analysis set.

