6.3.2. Secondary Endpoint #2 – Evaluation of Short-Acting Beta₂ Agonists Usage

6.3.2.1. Definition

Secondary endpoint #2 is the change from week 1 in the mean weekly SABA usage and the change from week 1 in the number of SABA-free days over the 12-week treatment period for the DS group. SABA usage and SABA-free days. Weekly average SABA use will be defined as ((number of inhalations in a week)*90 ug/7) and change from week 1 in weekly average SABA use will be defined as (week i – week 1). Weekly SABA-free days will be defined as number of days a patient does not use the rescue medication in a week. If no inhalations done for any week, the amount of the SABA use will be 0 and SABA-free days for week will 7.

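### No final data transfer is listed before inhalers are collected and the App removed, and the SAP does not separate a week without SABA use from a week without data

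*Protocol*

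**What the plan says.** **Visits.** For Visit 2, Protocol Appendix B lists "perform Albuterol eMDPI collection and accountability" and "remove the App from the patient's smart device". Table 3 has the same two items, and Section 5.1.1 says that "investigational center personnel will remove the App from the patient's smart device". Inhalers are also collected at the unscheduled dispensing visit. None of these places mentions pairing, uploading or checking the records first. On returned inhalers, Section 5.2.3 says "All empty, partially used, and unused inhalers will be collected at the end of the study and will be returned to the sponsor" or its designee; the stated purpose is reconciliation, and no data read-out is described.

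**Data path.** Section 5.1.1 says "The information from the eModule may be transmitted wirelessly (Bluetooth Low Energy) to an App". Section 5.1.2.1 describes receipt by the App as automatic over Bluetooth. Section 5.1.2.2 says the App-to-cloud link needs an internet connection. Each DS patient starts with 2 inhalers and may receive more.

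**Scoring.** SAP 6.3.2.1 defines weekly average use as inhalations in the week x 90 ug / 7, and change as week i minus Week 1. It adds: "If no inhalations done for any week, the amount of the SABA use will be 0 and SABA-free days for week will 7". No condition on data coverage is attached.

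**Related text.** SAP 5.2 has a disposition count for the "ITT analysis set who did not attempt to download the App". Protocol 5.1.1 gives 200 actuations per inhaler and notes that "the inhaler is equipped with a dose counter that shows only even numbers".

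**The concern.** An inhalation counts in the analysis only if its record travels from inhaler to App to cloud. If Bluetooth is off, the App is not working, or a second inhaler is kept away from the phone, the inhalation happens but the record does not arrive. When the site then takes the inhaler and deletes the App, the planned route for that record closes. The SAP rule turns the resulting silence into a definite value, and that value is the best possible score for the week.

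SABA use and SABA-free days are a named secondary objective, reported for the DS group alone. No control arm would show the same artefact, so a decline in connection could be read as a decline in rescue use. SAP 8.2 has the same weakness: a day with no recorded dose counts as zero, and a missing last record shortens the exposure period. SAP 8.3 handles the same data stream more safely, leaving flow parameters undefined in a week without inhalations.

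The point is limited to patients still on treatment. How weeks after discontinuation are scored is a separate question.

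**Working it through.** **Inputs from the documents:** weekly use = inhalations x 90 / 7; a week without inhalations scores 0 and 7; change = week i minus Week 1 (all SAP 6.3.2.1); 12 treatment weeks. **Assumed, because no document gives them:** the fraction m of patients whose week is wholly unsent, true inhalations per week, and true SABA-free days s.

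**Step 1, the plan's own figures.** With no recorded inhalation, 0 x 90 / 7 = 0 ug and 7 - 0 = 7 SABA-free days. Both are reproduced. An unsent week enters the formula exactly as an unused week does.

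**Step 2, one patient, one week.** Take 2 inhalations every day: true use is 14 x 90 / 7 = 180 ug/day, with 0 SABA-free days. If k days are unsent, scored use is 2 x (7 - k) x 90 / 7 and scored SABA-free days are k.

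| Unsent days k | Scored use (ug/day) | Scored SABA-free days |
|---|---|---|
| 1 | 154.3 | 1 |
| 3 | 102.9 | 3 |
| 5 | 51.4 | 5 |
| 7 | 0 | 7 |

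Only the wholly unsent week gives 0 and 7. A partly sent week is undercounted.

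**Step 3, group mean in a late week.** With full transmission in Week 1 and unchanged true use, the false change is -m x true use, and +m x (7 - s) SABA-free days.

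| Assumed true use; s | m = 5% | m = 10% | m = 20% |
|---|---|---|---|
| 7 inhalations/week (90 ug/day); 3 | -4.5 ug/day; +0.2 days | -9; +0.4 | -18; +0.8 |
| 14 (180 ug/day); 2 | -9; +0.25 | -18; +0.5 | -36; +1.0 |
| 28 (360 ug/day); 0 | -18; +0.35 | -36; +0.7 | -72; +1.4 |

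**Step 4, the sign.** Let m1 be the fraction unsent in Week 1 and mL the fraction in a late week. The false change in SABA-free days is (mL - m1) x (7 - s). With s = 3:
- Loss only late (m1 = 0, mL = 20%): 0.20 x 4 = +0.8 days, apparent improvement.
- Loss only in Week 1 (m1 = 20%, mL = 0): -0.20 x 4 = -0.8 days, apparent worsening.
- Equal loss: 0.

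A patient who never connects scores 0 ug in every week and 12 x 7 = 84 SABA-free days. The levels are wrong, but the change is 7 - 7 = 0.

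**The case against.** Several mitigating facts stand. Transfer to the App is described as automatic, the cloud synchronises automatically, and the eModule stores timestamped events, so a temporary gap may only delay records. Phone and inhalers should both be present at Visit 2, so a transfer may happen without being listed. Centers look at the dashboard at least weekly and could notice silence. Returned inhalers go to the sponsor and might be read later. The Study Pharmacy Manual, which holds device instructions, is not available here. All of this lowers the likely loss rate. None of it confirms or records that the data are complete, and the SAP uses no such confirmation.

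The SAP's wording refers to inhalations done, not received, and Protocol 9.3 restricts analysis to observed data unless the SAP says otherwise. One could argue that an unsent week is simply missing. That may be the intention, but the SAP gives the analyst no means of telling the two kinds of week apart.

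A reader might infer that non-transmission always favours the DS on this endpoint. That is true of weekly levels, not of change from Week 1, as Step 4 shows. Onboarding at Visit 1 makes later loss plausible, but no document establishes it. A reader might also take the SAP 5.2 disposition line as a forecast that some DS patients will never connect. It is only a reporting category: Protocol 5.1.1 makes downloading the App a condition of enrolment, with staff help. Nor do the documents say how the one dose required for the mITT set would be confirmed in a patient with no records.

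**Conclusion.** The concern holds as a gap in data capture combined with a scoring rule that hides it. No listed step secures or verifies the last transfer, and SAP 6.3.2.1 does not separate no use from no data received. For DS patients on treatment, weekly SABA use is biased down and SABA-free days up wherever records are unsent. The direction for change from Week 1 depends on when loss occurs.

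The size cannot be fixed from the documents. Under the stated assumptions (s = 3, complete Week 1, unchanged true use) the false gain is 0.2 days per week at m = 5% and 0.8 at m = 20%. Without loss the bias is zero.

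Secondary endpoint #2 is descriptive and DS-only, and the exposure summaries share the problem. It would be wrong to infer any effect on the ACT primary endpoint or its power, since ACT is a questionnaire completed at the center. The change is worth making because it is cheap and the artefact would otherwise go unseen.

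**What to change.** 1. **Protocol Table 3 and Appendix B (Visit 2/ET and unscheduled dispensing visits).** Before an inhaler is collected or the App removed, sync every used inhaler with the App and confirm upload to the cloud.
2. **SAP 6.3.2.1.** Score a week as 0 ug and 7 SABA-free days only when a transfer on or after the last day of that week covers each inhaler in use. Count an inhaler whose dose counter shows it is unused as covered; otherwise patients who never opened their second inhaler would be set to missing, and these are more likely to be low users. Set any other such week to missing, and report how many weeks are missing.
3. **Accountability.** For each inhaler, compare the dose-counter total (200 minus the reading) with the logged total, and list discrepancies above a prespecified threshold. The counter shows even numbers only and cannot assign doses to weeks, so this is a completeness check and not a source for imputation.

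The cost is a few minutes at visits already planned, some SAP wording, and some weeks set to missing.
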